#### **7.2.2 Serious adverse events (SAEs)**

A serious adverse event is any untoward medical occurrence or effect that

- results in death;
- is life threatening (at the time of the event);
- requires hospitalisation or prolongation of existing inpatients' hospitalisation;
- results in persistent or significant disability or incapacity;
- is a congenital birth defect; or
- any other important medical event that did not result in any of the outcomes listed above due to medical or surgical intervention but could have been based upon appropriate judgement by the investigator.

An elective hospital admission will not be considered as a serious adverse event.

For the above purpose LiPAT will keep a digital sAE-log which is accessible to the LiPAT investigational staff at all times. This sAE-log will be checked daily and discussed at the weekly LiPAT clinical monitoring meeting. In case of a sAE the principal investigator will be notified. In addition an internist is available for the investigational staff 24 hours a day to discuss any such sAE.

The sponsor will report the SAEs through the web portal *ToetsingOnline* to the accredited METC that approved the protocol, within 7 days of first knowledge for SAEs that result in death or are life threatening followed by a period of maximum of 8 days to complete the initial preliminary report. All other SAEs will be reported within a period of maximum 15 days after the sponsor has first knowledge of the serious adverse events.

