#### **6.3.1 Specific criteria for withdrawal (if applicable)**

If during the inclusion visit a severe carotid atherosclerotic plaque is discovered in the region of interest the participant will be withdrawn from the trial.

If during the duration of the trial any cardiovascular events occurs participants will be withdrawn from the trial.

If participation in the trial leads to uncontrollable hypo- or hyperglycaemia participants will be withdrawn from the trial.

If any other serious medical condition arises during the trial which requires medical specialty treatment or hospitalisation, participants will be withdrawn from the trial.

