### **7.2 AEs and SAEs**

#### **7.2.1 Adverse events (AEs)**

Adverse events are defined as any undesirable experience occurring to a subject during the study, whether or not considered related to trial procedure and the experimental intervention. All adverse events reported spontaneously by the subject or observed by the investigator or his staff will be recorded.

For the above purpose LiPAT will keep a digital AE-log which is accessible to the LiPAT investigational staff at all times. This AE-log will be checked daily and discussed at the weekly LiPAT clinical monitoring meeting. In addition, an internist is available for the investigational staff 24 hours a day to discuss any such AE.

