#### *Risks of specific measurements*

For LiPAT only non-invasive low risk study procedures will be performed. The investigational research team hold the opinion that the current protocol subscribes to the above and considers the risk for any adverse events due to the different study procedures low. Nevertheless it cannot wholly be excluded, that behavioural changes with regard to any changes in movement patterns may lead to unforeseen adverse events. LiPAT considers the risks in light of the recruited study population nevertheless acceptable.

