### **10.4 Annual progress report**

The sponsor/investigator will submit a summary of the progress of the trial to the accredited METC once a year. Information will be provided on the date of inclusion of the first subject, numbers of subjects included and numbers of subjects that have completed the trial, serious adverse events/ serious adverse reactions, other problems, and amendments.

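### The SAE definition exempts every elective admission, so a condition that arises or worsens during the trial and is serious only through a booked admission is classed as non-serious

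*Protocol*

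**What the plan says.** Section 7.2.2 lists the criteria that make an untoward occurrence serious. One is that it "requires hospitalisation or prolongation of existing inpatients' hospitalisation". The list does not separate emergency from planned admission. It ends with a residual criterion, "any other important medical event that did not result in any of the outcomes listed above due to medical or surgical intervention", which applies on the investigator's judgement. The sentence straight after the list reads: "An elective hospital admission will not be considered as a serious adverse event".

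The same section sets the reporting times to the METC. Fatal or life-threatening SAEs go within 7 days, with up to 8 more days to complete the report. All other SAEs go within 15 days.

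Other sections bear on the same events:

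- Section 7.2.1: "All adverse events reported spontaneously by the subject or observed by the investigator or his staff will be recorded".
- Section 7.3: every adverse event is followed until it resolves or stabilises.
- Section 6.3.1: "If any other serious medical condition arises during the trial which requires medical specialty treatment or hospitalisation, participants will be withdrawn from the trial".
- Section 10.4: the annual METC report covers "serious adverse events/ serious adverse reactions, other problems, and amendments", along with recruitment and completion numbers.

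**The concern.** An exemption for elective admissions has a sound purpose. It keeps an operation that was already on the waiting list at enrolment from being counted as harm. That purpose needs two conditions: the admission was planned before randomisation, and the underlying condition has not worsened since. The protocol states neither. Its exemption turns on how the admission is arranged, not on when the condition arose.

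This matters because section 9.3 accepts that "any changes in movement patterns may lead to unforeseen adverse events", and participants are observed for 12 months. That leaves time for a complaint to develop, be referred and be admitted by appointment. Several exclusions in section 4.3 (severe joint complaints, foot ulcers, peripheral arterial disease, ischaemic heart disease) look back only three months, so people with an older history can enrol. What is at stake is whether such an event is labelled serious and reaches the METC promptly.

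**Working it through.** No figure is involved, so the check is textual. There were two questions: does any part of the protocol limit the exemption, and what happens to each kind of event when the sections are applied together?

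**Step 1: search for a limit.** No section restricts the exemption to admissions that were pre-planned, for pre-existing conditions, or scheduled before consent or enrolment. Elective is not defined anywhere.

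**Step 2: apply the sections as written.**

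| Event during the trial | SAE under 7.2.2? | METC report within 7 or 15 days? | Can 6.3.1 withdraw the participant? |
|---|---|---|---|
| A. New serious condition, emergency admission | Yes, through hospitalisation | Yes | Yes |
| B. Admission booked before randomisation, condition unchanged | No, exempt | No | Not under this rule; the condition did not arise in the trial |
| C. New serious condition, booked admission, no other seriousness criterion met | No, exempt | No | Yes |
| D. As C, but also fatal, life threatening, disabling or judged medically important | Can still be an SAE through that criterion | Yes, if so classed | Yes |
| E. New serious condition, specialist outpatient treatment only | Not through hospitalisation | Only if another criterion applies | Yes |

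**Step 3: compare the rows.** Row B is what an elective exemption is meant to remove. Row C is removed by the same sentence. A and C can be the same condition and differ only in how the admission was arranged. A pre-existing condition that worsens after randomisation and is then admitted by appointment also loses SAE status.

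**Step 4: what happens to a row C event.** It is recorded under 7.2.1, in a log that is checked daily and discussed weekly, and followed under 7.3. If the participant is withdrawn, the reason is logged (section 6.3, on withdrawal of individual subjects). Section 6.5 adds a questionnaire on whether a condition caused by participation lay behind the withdrawal. The participant may decline further contact. None of these steps turns the event into an SAE or starts the 15-day period.

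The defect is therefore row C, together with its counterpart for worsened pre-existing conditions.

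**The case against.** The strongest reply is that the sentence exempts an admission, whereas an SAE is an untoward medical occurrence. On that reading the underlying condition could still be judged against the list. The reading is possible, but the sentence does not state it and it follows directly on a list that contains the hospitalisation criterion. Where hospitalisation is the only criterion met, setting the admission aside leaves nothing to make the event serious. A reporting rule that can be read in two ways needs clarifying in any case.

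A second reply is that the criterion for important medical events rescues these cases. It may rescue some, but only case by case, against an exemption stated without exceptions.

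A third reply is that the protocol has other safeguards: adverse event recording and follow-up, logged withdrawal reasons, the questionnaire in 6.5, and the heading for other problems in the annual report. This stands, and it limits the consequence. A reader might infer that such events vanish, or that the METC can learn of SAEs only. Neither follows. What is lost is the serious label and the 15-day report, not every route to the METC.

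A reader might also see a flat contradiction between 6.3.1 and 7.2.2. The text does not support that. Withdrawal is also triggered by specialist treatment without admission (row E), so its threshold is wider than the SAE definition even without the exemption. Row C shows the effect of the exemption; it does not show that the two sections conflict.

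**Conclusion.** The point holds within a narrow scope. The exemption is wider than its purpose. As written, it makes a non-serious adverse event of any condition that arises or worsens during the trial and is serious only through a scheduled admission. The conclusion rests on the ordinary reading of the sentence and on the absence of any limit elsewhere in the protocol.

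The size cannot be given as a number. The protocol states no expected admission rate and no share of admissions made by appointment. If no such admission occurs, nothing is lost.

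Two wider inferences should not be drawn:

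- The statement in section 9.3 that risk is low is not undermined by an incomplete count. It is a judgement made in advance, mainly about the study procedures, and rests on no count.
- No bias in a comparison of SAEs between arms can be claimed. Section 8 specifies no such table or analysis, and the exemption applies to both arms alike.

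The primary and secondary efficacy analyses are not affected. This is a fault in a safety-reporting definition, and correcting it is worthwhile because it is cheap.

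**What to change.** Replace the exemption sentence in 7.2.2 with: *A hospital admission already planned before randomisation, for a pre-existing condition that has not worsened since, is not considered a serious adverse event; a planned admission for a condition that arose or worsened after randomisation is.*

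Add to 6.3.1 that any event leading to withdrawal through hospitalisation is assessed against the SAE definition. This leaves the withdrawal rule itself unchanged and only ensures that the seriousness assessment is made and recorded.

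The cost is an amendment of one sentence and a cross-reference, matching instructions for staff who complete SAE forms, a few more forms, and possibly a slightly higher SAE count. No visit, measurement or treatment changes.

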### **7.3 Follow-up of adverse events**

All AEs will be followed until they have abated, or until a stable situation has been reached. Depending on the event, follow up may require additional tests or medical procedures as indicated, and/or referral to the general physician or a medical specialist.

SAEs need to be reported till end of study within the Netherlands, as defined in the protocol.

## **8. STATISTICAL ANALYSIS**

The significance levels used in the statistical analyses will be 0.05. The validity of the normality assumption will be checked for all outcomes. Baseline characteristics will be compared between the intervention and the control group. For continuous variables (e.g. age, BMI) mean and standard deviations will be presented; numbers and percentages will be shown for categorical variables (e.g. smoking, medication use). T-tests will be used to compare differences in continuous baseline characteristics between the intervention and control group and chi-square test will be used for categorical variables. Assuming that the randomization was successful no differences are expected. Missing data will be imputed using multiple imputations techniques.

### **8.1 Primary study parameter(s)**

The effect of the intervention on the primary outcome PWV at month 6 will be analysed using intention-to-treat (ITT) approach according to randomization assignment. The ITT analyses will be used as primary method for our statistical analyses and any outcomes in our reports will be primarily based upon these ITT analyses. In addition, a per protocol analysis will be performed for those who attended the workshops. These analyses will be used to gain some insights into any potential non-response / drop out. These per protocol analyses will not be the primary source for reporting outcomes. General linear models will be used to analyse the effect of the intervention on PWV at month 6. Due to the COVID-19 crisis some month 6 measurement will take place at a later moment, depending on the duration of this delay we will have to adjust for this in our statistical analyses. In addition, repeated measures will be taken into account, baseline, month 3, and month 6 using mixed models in SPSS. The 3-month visits might be missing for some participants due to COVID-19 crisis, we assume that the 6-month measurements for these participants can take place as planned. In these models, subject is entered as a random effect and intervention (categorical variable with 2 levels: 1: intervention; 2: control group) as a fixed effect. The baseline value of PWV and sex will be used as covariates in analyses.

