### **8.2 Secondary study parameter(s)**

Sedentary time, as measured by the activPAL will be analysed as total sedentary minutes on an average day as well as the percentage of sedentary during wake time. Similarly, time standing and stepping, also derived from the activPAL data will be analysed. All metabolic health parameters and microcirculation measurements will also be analysed as continuous

variables. Quality of life and mental functioning are also analysed as continuous variables. Finally, measures of body composition measures are also all continuous outcomes variables

Similar to the primary outcome analyses, general linear mixed models will be used to analyse the change in the secondary outcome measures from baseline to month 6. Using mixed models, the repeated measures will be taken into account similar to the analyses with the primary outcome.

All analyses, for the both primary and secondary outcomes will also be conducted for the follow-up (month 12 data) to examine the long-term effect of the intervention, taking into account all repeated measures (baseline, month 3, month 6) in a mixed model.

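### The added mixed model in 8.1 keeps baseline PWV as a response row with one intervention effect and no visit interaction, so it reports about two thirds of the effect

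*Protocol*

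**What the plan says.** Protocol section 8.1 describes two analyses of PWV. The first is cross-sectional: "General linear models will be used to analyse the effect of the intervention on PWV at month 6". The second is longitudinal: "In addition, repeated measures will be taken into account, baseline, month 3, and month 6 using mixed models in SPSS". The longitudinal model is then specified: "In these models, subject is entered as a random effect and intervention", a two-level factor, "2: control group) as a fixed effect". No visit effect and no intervention-by-visit effect is named. The paragraph closes with "The baseline value of PWV and sex will be used as covariates in analyses", and makes no exception for the mixed model. The section also expects gaps at month 3: "The 3-month visits might be missing for some participants due to COVID-19 crisis".

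Section 8.2 extends the approach to the secondary outcomes: "Using mixed models, the repeated measures will be taken into account similar to the analyses with the primary outcome". For month 12 it covers primary and secondary outcomes, "taking into account all repeated measures (baseline, month 3, month 6) in a mixed model".

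**The concern.** Taken literally, baseline PWV appears twice in the longitudinal model: as one of three response rows per participant and as a covariate. Randomisation follows the baseline measurements, so the true intervention effect on the baseline row is zero, and once baseline is conditioned on, the estimated effect there is exactly zero. A model with a single intervention coefficient averages that zero with the effects at months 3 and 6. The reported number is then not the effect at month 6, nor the average effect on treatment, but a diluted mixture.

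The obvious repair, an intervention-by-visit term, does not suffice while baseline stays on both sides. The baseline row is fully explained by the covariate with slope 1. The later rows have a smaller slope and real residual scatter. A common slope and a common residual variance cannot describe both, and the standard error suffers.

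At stake are the size of the effect and its interval wherever this model is the one reported.

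**Working it through.** **Inputs.** From the protocol: at least 73 per group, alpha 0.05 (two-sided by the printed formula), power 80% (section 4.4); responses at baseline, month 3 and month 6; random subject effect; one intervention effect; baseline as covariate (section 8.1). Assumed, because the protocol gives no figure: equal variance at all visits (set to 1) and an equal correlation r between any two visits, taken over 0.3 to 0.9.

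**The planned effect in SD units.** The 73 per group cannot be reproduced, because no mean or SD of PWV is given. It can be inverted: (1.960 + 0.842) × √(2/73) = 2.802 × 0.1655 = 0.464 SD. This only sets the scale; the dilution factor does not depend on it.

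**Model as written.** With complete data, the intervention coefficient of a random-intercept model is the regression of each participant's mean, (Y0 + Y3 + Y6)/3, on arm and Y0. Since Y0 is itself a regressor, its share adds nothing to the arm coefficient:

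- coefficient = (0 + d + d)/3 = 2d/3 = 2 × 0.464/3 = 0.309 SD
- SE = (2/3) × √(2/73) × √[(1 − r)(1 + 2r)/2]
- r = 0.5: 0.667 × 0.1655 × 0.707 = 0.078
- r = 0.8: 0.667 × 0.1655 × 0.510 = 0.056

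The shortfall is 0.464 − 0.309 = 0.155 SD. Approximate coverage of the true effect is Φ(1.96 − 0.155/SE), which is about 49% at r = 0.5 and 22% at r = 0.8. Simulation (8,000 trials per scenario) gave mean estimates of 0.308 to 0.310 and coverage of 50%, 37%, 23% and 4% at r = 0.5, 0.7, 0.8 and 0.9. Type I error was 0.048 to 0.050: estimate and SE shrink by the same two thirds, so the t statistic equals that of a model on months 3 and 6 alone.

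**What the covariate contributes.** Drop it, keep the three response rows, and the coefficient is still 2d/3 on average (0.307 to 0.309 in simulation). Only the SE changes, to √(2/73) × √[(1 + 2r)/3]: 0.135 at r = 0.5 and 0.154 at r = 0.8. The same coverage formula then gives about 79% and 83%. So the dilution comes from the baseline response row without an interaction, and the covariate tightens the interval around the diluted value.

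**Other visit patterns.** By the same averaging the factor is (0 + d)/2 = 1/2 for a participant with no month-3 row, and (0 + 3d)/4 = 3/4 if month 12 is a further response. If month 3 is filled in by the multiple imputation planned in section 8, the factor stays 2/3.

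**Adding visit main effects only.** Nothing changes: still 2/3, type I error still about 5%.

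**Adding intervention-by-visit, baseline still on both sides.** The month-6 estimate is right on average (0.460 to 0.464). Its SE is not:

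- the fitted common slope is b = (1 + 2r)/3, so the true variance factor is 1 − 2br + b²
- the model uses (1 − r) + τ², with τ² = (1 − r)[(2/3)(1 + 2r) − 1]/3
- r = 0.5: b = 0.667, true 0.778, model 0.556; SE ratio √(0.556/0.778) = 0.845
- r = 0.8: b = 0.867, true 0.364, model 0.249; SE ratio √(0.249/0.364) = 0.826

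Type I error is 2[1 − Φ(1.96 × ratio)] = 0.098 and 0.105. Over r = 0.3 to 0.9 the ratio runs from 0.861 to 0.821 and type I error from 0.091 to 0.108. Simulation over 0.5 to 0.9 gave 0.100 to 0.110, with coverage of 89 to 90%.

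**Post-baseline responses only, baseline as covariate, intervention-by-visit included.** Mean month-6 estimate 0.460 to 0.465, type I error 0.050 to 0.052, coverage about 95%. The month-6 general linear model does as well (type I error 0.051 to 0.053).

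**The case against.** Four points limit the concern, and all of them stand.

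- A reader might infer that the main PWV result is biased. It is not: the month-6 general linear model is named first, and with baseline as covariate it is ordinary ANCOVA.
- A reader might infer that the model as written produces false positives. It does not; its null test holds at about 5%. The 10 to 11% belongs to a model with an intervention-by-visit term, which the protocol does not contain. It matters as a warning about the natural repair.
- The two-thirds dilution is not caused by using baseline twice. It arises equally without the covariate.
- A reader might infer that every secondary and month-12 result certainly uses this model. Section 8.1 names only the baseline value of PWV as covariate, and 8.2 says only that the approach is similar, so the extension depends on how 8.2 is read.

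There is also a case that taking repeated measures into account is loose wording. The month-12 list in 8.2 omits month 12 itself, so it cannot be a literal list of responses, and baseline may have been meant as covariate only. That reading is possible and would be correct statistically, but 8.1 does not say it: baseline is listed on the same footing as months 3 and 6, and the covariate sentence follows the mixed-model specification without restriction. If the looser reading was intended, the text still needs to say so.

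**Conclusion.** The concern holds for the additional repeated-measures model in 8.1. As written, it returns two thirds of a constant month-3 and month-6 effect: about 0.31 SD for a true 0.464 SD. Its interval misses the true effect in about half of trials at correlation 0.5 and in nearly four fifths at 0.8. The two-thirds factor needs complete data and an equal effect at both visits, but no assumption about correlation. The coverage figures do depend on the assumed correlation and on 73 per group.

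The defect concerns estimation in a supporting PWV model. It reaches the secondary outcomes and month 12 if 8.2 is read the same way; there the mixed model is the stated method and no separate sound model is clearly named. The warning about the partial repair is robust: the standard error shortfall is similar across correlations of 0.3 to 0.9.

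**What to change.** In 8.1, state that the responses in the mixed model are months 3 and 6 only. Keep the baseline value and sex as covariates, include visit and intervention-by-visit terms, and name the month-6 contrast as the reported estimate. In 8.2, say the same for each secondary outcome with that outcome's own baseline value, and for follow-up add month 12 as a response and report the month-12 contrast.

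An equivalent alternative keeps baseline as a response, constrains the two arms to a common baseline mean, and drops baseline as a covariate.

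Either option costs about a sentence in each section. It needs no new data and no change to visits or sample size, and should be settled before the data are analysed.

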### 4.4 Sample size calculation

For the primary objectives of the study:

to be able to detect a 10% difference in PWV after the intervention between the intervention group and the control group set against a probability of a type 1 error at 0.05 (i.e.,  $\alpha$ ) and the ability to detect a true difference between the intervention group and the control group set at 80% (i.e.,  $\beta$ ) both groups should consist of a minimum of 73 participants each. These estimates are conservative taking into account only PWV values at entry and exit of the trial. The 10% difference is speculative and based upon a mean PWV estimates from The Maastricht Study data as there is currently no data available on LiPA and arterial stiffness. For reasons of efficiency in addition to potential drop (roughly estimated at 10%) out we will include in each group 80 participants

to be able to detect a 10% difference in carotid distensibility after the intervention between the intervention group and the control group set against a probability of a type 1 error at 0.05 (i.e.,  $\alpha$ ) and the ability to detect a true difference between the intervention group and the control group set at 80% (i.e.,  $\beta$ ) both groups should consist of a minimum of 73 participants each. These estimates are conservative taking into account only carotid distensibility values at entry ( $t = 0$ ) and exit of the investigational period of the trial ( $t = 6$ ). The 10% difference is speculative and based upon mean estimate from The Maastricht Study data as there is currently no data available on LiPA and arterial stiffness. For reasons of efficiency in addition to potential drop (roughly estimated at 10%) out we will include in each group 80 participants.

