#### According to:

$$K = n_2 / n_1$$

$$n_1 = ((\sigma n_1)^2 + ((\sigma n_2)^2) / k) / (Z_{1-\alpha/2} + Z_{1-\beta})^2 / \delta^2$$

$$n_1 = x ; n_2 = K n_1$$

$\delta = |\mu_2 - \mu_1|$  = absolute difference between two means

$\sigma_1, \sigma_2$  = variance of mean 1 and 2

$n_1$  = sample size for group 1

$n_2$  = sample size for group 2

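### The mixed models name only a random subject effect; if nothing is added, month-6 and month-12 contrasts can have standard errors that are too small when correlation declines or variance grows over time

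*Protocol*

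**What the plan says.** Protocol 8.1 gives PWV at month 6 two analyses. The first is a single-visit model: "General linear models will be used to analyse the effect of the intervention on PWV at month 6". The second, introduced as an addition, is a mixed model in SPSS on baseline, month 3 and month 6. For it the protocol states: "In these models, subject is entered as a random effect". Intervention is the fixed effect, and baseline PWV and sex are covariates. No random slope, residual covariance structure or robust standard error is named, and no visit or arm-by-visit term.

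Protocol 8.2 uses mixed models for the change in the secondary outcomes to month 6. It then repeats the analyses of all primary and secondary outcomes at month 12, "taking into account all repeated measures (baseline, month 3, month 6) in a mixed model". Section 8 sets the level: "The significance levels used in the statistical analyses will be 0.05". Section 3 places the visits at months 0, 3, 6 and 12. The protocol gives no between-visit correlation and no SD by visit for any outcome.

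**The concern.** A random subject effect with independent residuals implies one variance for all visits and one correlation for every pair of visits, whether 3 or 12 months apart. If baseline predicts month 12 less well than month 3, the variance left after baseline adjustment grows with time. The model replaces it by its average over visits, which is too small for the last visit and too large for the first.

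The design makes such a pattern plausible, though it does not prove it. The visits are unequally spaced. Section 5.1 ends the planned phone calls after month 3 and leaves months 6 to 12 unsupervised. Section 8.1 expects some month-6 visits to be delayed.

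At stake are the confidence intervals and tests for the long-term effect at month 12 and for the secondary outcomes at month 6, wherever these come from the mixed model.

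**Working it through.** **Inputs**

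| Input | Value | Source |
|---|---|---|
| Significance level | 0.05, two-sided | Section 8; formula in 4.4 |
| Evaluable per arm | 73 (80 enrolled) | 4.4 |
| Visits | 0, 3, 6, 12 months | Section 3 |
| Within-subject structure | random subject effect | 8.1 |
| Correlations, SD by visit | not given | assumed below |

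**The plan's own figure.** Section 4.4 says "both groups should consist of a minimum of 73 participants each". It gives no SD (the formula names only "variance of mean 1 and 2"), so 73 can only be solved backwards. From the standard formula n = 2(1.96 + 0.84)²(SD/δ)², SD/δ = √(73 / (2 × 7.849)) = 2.16, which is an SD of about 21.6% of the mean for a 10% difference. Here 73 serves only as the arm size. The standard-error ratio below depends on neither the SD nor n.

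**Closed form.** Take unit variance at each visit, baseline as covariate with a common slope, visit and arm-by-visit terms, and complete data. Let r_j be the correlation of visit j with baseline and b the mean of the r_j.

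- Residual variance at visit j: v_j = 1 + b² − 2·b·r_j
- Model SE / true SE at visit j: √(mean of v / v_j)
- False-positive rate: 2·(1 − Φ(1.96 × ratio))

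Worked case, r = 0.80/0.75/0.65 at months 3/6/12: b = 0.733, so v = 0.364, 0.438, 0.584, with mean 0.462. At month 12 the ratio is √(0.462/0.584) = 0.889 and the rate is 2·(1 − Φ(1.743)) = 8.1%.

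| Assumed r with baseline | Last visit | SE ratio | Closed form | Simulated |
|---|---|---|---|---|
| 0.80/0.75/0.65 | month 12 | 0.889 | 8.1% | 7.7% |
| 0.80/0.70/0.55 | month 12 | 0.863 | 9.1% | 9.5% |
| 0.80/0.75 | month 6 | 0.955 | 6.1% | 6.9% |
| 0.80/0.70 | month 6 | 0.924 | 7.0% | 7.2% |
| flat 0.75 | last | 1.000 | 5.0% | 5.2% |

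Each simulated rate uses 6,000 trials with 73 per arm, so its Monte Carlo standard error near 5% is √(0.05 × 0.95 / 6000) = 0.3 percentage points.

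**Wider range of patterns.** Same random-intercept model with the last-visit contrast (sex left out), 6,000 trials each:

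| Assumed pattern | Month 6: ratio, rate | Month 12: ratio, rate |
|---|---|---|
| Constant correlation 0.7, equal SD | 1.005, 5.1% | 1.003, 4.9% |
| Constant correlation 0.5, equal SD | 1.005, 4.7% | 1.000, 5.1% |
| Decay to 0.9 per 3 months | 0.877, 8.6% | 0.798, 12.0% |
| Decay to 0.8 per 3 months | 0.893, 8.2% | 0.832, 10.5% |
| Decay to 0.7 per 3 months | 0.923, 7.4% | 0.880, 8.5% |
| Stable part plus partial decay | 0.980, 5.7% | 0.930, 6.5% |
| Random slopes, SD 0.5 at 12 months | 0.980, 5.8% | 0.890, 8.3% |
| Random slopes, SD 1.0 at 12 months | 0.931, 7.0% | 0.800, 11.4% |
| SD rises 15% by last visit | 0.976, 5.9% | 0.949, 6.2% |
| SD falls 15% by last visit | 1.042, 4.1% | 1.047, 4.1% |

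**Comparators in the same runs.** A single-visit covariance-adjusted analysis held 4.6% to 5.8% in every pattern, with ratios 0.985 to 1.011. With complete data it is equivalent to an unstructured model with a baseline slope for each visit. The visit-averaged coefficient of the random-intercept model had ratios 0.986 to 1.009.

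**Baseline as a response.** Section 8.1 lists baseline among the repeated measures as well as among the covariates. If it is fitted as a response and the contrast is change from baseline, the closed-form rates under the three decay patterns are 9.5-10.5% at month 6 and 11.0-13.6% at month 12, and 5.0% under constant correlation.

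**The case against.** The case against is substantial, and most of it limits the point.

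- **No excess is proven.** A reader might infer that the standard error is always too small. The protocol gives no correlations or visit-specific SDs. Constant values give a correct standard error, and falling variance gives one that is too large. This stands: the point is conditional.
- **Month-6 PWV has its own model.** A reader might infer that the main month-6 PWV result is compromised. Section 8.1 names a single-visit general linear model first, and that does not depend on correlation between visits. This stands in full.
- **The mixed model as listed has no arm-by-visit term.** Taken literally it estimates an average over visits, whose standard error is right with complete data. This also stands. But 8.1 and 8.2 seek effects at month 6 and month 12, and reading those from the mixed model requires such a term. The problem arises once it is added.
- **Silence is not exclusion.** The wording does not rule out a residual covariance alongside the random effect, and an SAP not shown may specify one. This is why the point begins with a condition. Still, the protocol has written down one structure, so the remark concerns a stated choice and not only an omitted detail.
- **Not every outcome need suffer.** A reader might infer more false claims across all secondary outcomes. These range from HbA1c and weight to questionnaires and skin flowmetry, and nothing shows that all share a declining correlation.
- **Complete data were assumed.** The protocol expects missing month-3 visits, late month-6 visits and multiple imputation, so the rates do not transfer exactly.

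**Conclusion.** The point holds in conditional form. If the random subject effect is the only structure used and a month-6 or month-12 effect is taken as a visit-specific contrast, declining correlation or growing variance makes its standard error about 2-12% too small at month 6 and 5-20% too small at month 12. The false-positive rate is then about 6-9% and 6-12%. These ranges rest on assumed covariance patterns, baseline as a covariate, 73 per arm and complete data.

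The exposed analyses are the additional mixed model for PWV at month 6, the secondary outcomes at month 6, and all outcomes at month 12. The change is worth making because a structure that holds the 5% level under every pattern tried is available at almost no cost.

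**What to change.** For the mixed models in 8.1 and 8.2, replace the random subject intercept by an unstructured residual covariance over the post-baseline visits (SPSS MIXED, REPEATED by visit within subject, with Satterthwaite or Kenward-Roger degrees of freedom). Keep baseline as a covariate only. Include visit, arm-by-visit and baseline-by-visit terms, and report the month-6 and month-12 contrasts from that model. The single-visit model for PWV at month 6 can stay as written.

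The cost is analysis wording. With T post-baseline visits the covariance has T(T+1)/2 parameters: 3 for months 3 and 6, and 6 for months 3, 6 and 12, against 2 for a random intercept. The planned 146 evaluable (2 × 73) to 160 enrolled participants support that. The month-12 interval may become somewhat wider, which is the correct result if correlation declines.
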